## POST SURVEY

Please answer the following regarding the intensity or strength of the aroma inhaler.

1. On a scale of 1 to 10 rate overall how enjoyable the aroma of the inhaler was (0 being not enjoyable at all and 10 being very enjoyable)

0	1	2	3	4	5	6	7	8	9	10
---	---	---	---	---	---	---	---	---	---	----

2. On a scale of 1 to 10 rate the usual strength smell of the aroma inhaler (0 being no strength and very weak to 10 the strongest it could be)

0	1	2	3	4	5	6	7	8	9	10
---	---	---	---	---	---	---	---	---	---	----

3. How likely are you to continue to use this aroma inhaler (1 being not at all likely and 10 being very likely)?

0	1	2	3	4	5	6	7	8	9	10
---	---	---	---	---	---	---	---	---	---	----

4. Any other thoughts you wish to share about this experience?

Thank you for taking the time to complete this study, please return this and all other surveys and the logbook in the prepaid envelope. Once this is received, a gift card will be sent. If you have any further questions, please contact [name] at [[contact]](mailto:[contact])

## Appendix B

### SAFETY DATA SHEET

Firefox

about:blank

#### Plant Extracts International Inc.

[name]  
[contact]-H2EO [contact]) or [contact]  
[contact]-H2EO [contact]) or [contact]

[www.plantextractsinc.com](http://www.plantextractsinc.com) [[contact]](mailto:[contact])

Nurse/Practitioner Safety Data Sheet	BERGAMOT ESSENTIAL OIL SDS #004
Company Name: Plant Extracts International Inc. [name]	Product Name: Bergamot Essential Oil Source: Citrus bergamia (bergapten-free) Physical state: Essential oil Major constituents: limonene, linalyl, acetate, linalool
For reference in handling: – Bath Salts – Aethereo®Sticks – Massage Oils – Mask Sprays – AromaDiscs (for use with fan diffuser) – Quantities of 30 mL (1 oz.) or less*	Handling and Storage: Store in sealed containers in cool, dry area. Avoid exposure to heat, light, and moisture.  *For larger quantities refer to manufacturer's or formulator's SDS
Aroma: Spicy/citrus/floral  Physical data: Solubility: 20 mg/L in water; soluble in most organic solvents.  Toxicological Information: Ingestion: May be harmful if swallowed Contact with eyes: Irritating to eyes Contact with skin: Use in <3% dilution in fractionated coconut oil	Health and Hazard Data:  Eyes: Will cause irritation. Flush with milk or water. Contact physician if needed. Skin: Wash affected areas thoroughly with water and soap. Contact physician if needed. Ingestion: Rinse mouth with milk or water. Do not induce emesis. Contact a physician immediately. Inhalation: For use in personal inhalers or for room diffusion.
Spill, leak, and disposal procedures: Soak up with inert absorbent/paper and dispose according to regulations	Emergency First Aid Procedure: Follow normal first aid procedure. Contact doctor or poison control as needed.
Ecological information: The product is not harmful in the local environment in the quantities available. Limited potential for bio-accumulation.	– This product is for external use, and low level inhalation. It is not intended for enteral ingestion. – Keep away from eyes.
Exposure Scenarios: Bath Salts: 0.154 mL per average bath Aethereo®Sticks: 0.83 µL per average inhalation Massage Oils: 0.2 mL per average treatment AromaDiscs: 0.17 µL per average inhalation Mask Sprays: 1.82 µL per hour @ average respiration rate.	– Plant Extracts International disclaims any warranty expressed or implied as well as any liability for any injury or loss arising from the use of this information or the material described. – These data are condensed from the manufacturer's Safety Data Sheet for this product. – It is the responsibility of the user to determine appropriate precautions for the safe handling and use of this product. – This safety data is specific to the product designated above, as supplied by Plant Extracts International Inc.

October 2020

Copyright © 2020 Plant Extracts International Inc.

# MANUFACTURER SAFETY DATA SHEET

Firefox

about:blank

## BERGAMOT ESSENTIAL OIL SAFETY DATA SHEET #004 - MANUFACTURING

### 1. Company/Product Identification

Company: Plant Extracts International Inc.  
[name]  
[contact] [contact]  
E-mail Address: [[contact]](mailto:[contact])  
Identified Uses: Manufacture of essential oil products  
Natural Product: Yes  
Chemical Identity: Essential oil  
Commercial Name: Bergamot Essential Oil  
FEMA: 2153  
Scientific Name/Plant of Origin: Essential oil from the peel of *Citrus bergamia* (bergapten-free)  
Major Constituents: limonene, linalyl acetate, linalool

### 2. Hazard Identification

Pictograms/Signal words:

#### Warning

Hazard Statements:

H226 – flammable liquid  
H303 – may be harmful if swallowed  
H316 – causes mild skin irritation  
H320 – causes eye irritation

Precautionary Statements:

P210 – keep away from heat/sparks/open flame  
P233 – keep container tightly closed  
P235 – keep cool  
P313 – if severe irritation occurs/persists: get medical advice/attention  
P370 + P378 – in case of fire: use dry sand, dry chemical or alcohol-resistant foam for extinction

### 3. Composition/Information on Ingredients

Ingredient(s): Essential oil of *Citrus bergamia*  
CAS Nr.: 8007-75-8  
CTFA Nr.: 296-429-8  
Concentration: 100%

### 4. First Aid Measures

General Indications:

Remove contaminated clothing.  
If dizzy or lightheaded from exposure, leave the area until normalcy is regained.

Skin Exposure:

Wash skin with soap and warm water.  
Use eyeglass with milk, if available; otherwise flush with water.

Eye Exposure:

Administer milk, or charcoal tablets if available.

Ingestion:

None identified.

Main Hazard:

May cause conjunctival irritation.

October 2020

Copyright © 2020 Plant Extracts International Inc.

# Safety Data Sheet and GAS CHROMATOGRAPHY/MASS SPECTROMETRY (GC/MS)

Firefox

about:blank

[figure not shown]
The Australian Essential Oil Company & Plant Extracts International Inc.

## ANALYTICAL DATA SHEET **Bergamot**

*Citrus bergamia* (bergaptene-free)

### Gas Chromatographic Trace

### Constituent Mass Balance

RT (min)	Area %	Component
4.779	0.29	alpha-thujene
4.917	1.46	alpha-pinene
5.277	0.05	camphene
5.952	1.00	sabinene
5.998	7.20	beta-pinene
6.507	0.64	myrcene
6.845	0.04	alpha-phellandrene
7.188	0.11	alpha-terpinene
7.434	2.39	para-cymene
7.554	38.36	limonene
8.247	0.12	trans-beta-ocimene
8.493	6.69	gamma-terpinene
9.454	0.28	terpinolene
9.918	11.70	linalool
14.930	0.04	trans-sabinene hydrate acetate
15.090	29.20	linalyl acetate
20.074	0.25	beta-caryophyllene
20.704	0.1	trans-alpha-bergamotene

Mass balance: 100% (w/w)

### Physical Data

Relative Density @ 25°C: 0.848  
Refractive Index @ 25°C: 1.4735  
Optical Rotation @ 25°C: +62.47°

### Date of Manufacture

Date of GC run for specific batch

### Product Life

3 years from the date of analysis, when stored under appropriate conditions

### GC and Run Parameters

Hewlett Packard HP 6890 Series GC System  
Detector: HP5973 Mass Selective Detector  
Column: HP-5 (30 m x 0.32 mm x 0.25 µm film thickness)  
Temperature Program: 0-2 min @ 50°C, 50 - 300°C @ 4°C/min  
Carrier Gas: Helium  
Injection: 1.0 µL (1:100 dilution in MeOH)

A mass balance (weight for weight) of 100% indicates a pure and natural essential oil.

These data are aggregated from the last five batch analyses.

Specific batch data is available from the relevant certificate of analysis.

© 2022 by Plant Extracts International Inc.

All rights reserved. Reproduction or retransmission to third parties is expressly forbidden.

# FDA TRIAL REGISTRATION BERGAMOT

CFR - Code of Federal Regulations Title 21

<https://www.accessdata.fda.gov/scripts/cdrh/cfdocs/cfcfr/cfrsearch.cfm?..>

[FDA Home](#) [Medical Devices](#) [Databases](#)

## CFR - Code of Federal Regulations Title 21

**The information on this page is current as of Jul 20, 2022.**

For the most up-to-date version of CFR Title 21, go to the [Electronic Code of Federal Regulations \(eCFR\)](#).

[New Search](#)

[Help](#) | [More About 21CFR](#) 

[Code of Federal Regulations]  
[Title 21, Volume 3]  
[CITE: 21CFR182.20]

TITLE 21--FOOD AND DRUGS  
CHAPTER I--FOOD AND DRUG ADMINISTRATION  
DEPARTMENT OF HEALTH AND HUMAN SERVICES  
SUBCHAPTER B - FOOD FOR HUMAN CONSUMPTION (CONTINUED)  
PART 182 -- SUBSTANCES GENERALLY RECOGNIZED AS SAFE

Subpart A - General Provisions

Sec. 182.20 Essential oils, oleoresins (solvent-free), and natural extractives (including distillates).

Essential oils, oleoresins (solvent-free), and natural extractives (including distillates) that are generally recognized as safe for their intended use, within the meaning of section 409 of the Act, are as follows:

Common name	Botanical name of plant source
Alfalfa	Medicago sativa L.
Allspice	Pimenta officinalis Lindl.
Almond, bitter (free from prussic acid)	Prunus amygdalus Batsch, Prunus armeniaca L., or Prunus persica (L.) Batsch.
Ambrette (seed)	Hibiscus moschatus Moench.
Angelica root	Angelica archangelica L.
Angelica seed	Do.
Angelica stem	Do.
Angostura (cusparia bark)	Galipea officinalis Hancock.
Anise	Pimpinella anisum L.
Asafetida	Ferula assa-foetida L. and related spp. of Ferula.
Balm (lemon balm)	Melissa officinalis L.
Balsam of Peru	Myroxylon pereirae Klotzsch.
Basil	Ocimum basilicum L.
Bay leaves	Laurus nobilis L.
Bay (myrcia oil)	Pimenta racemosa (Mill.) J. W. Moore.
Bergamot (bergamot orange)	Citrus aurantium L. subsp. bergamia Wright et Arn.
Bitter almond (free from prussic acid)	Prunus amygdalus Batsch, Prunus armeniaca L., or Prunus persica (L.) Batsch.
Bois de rose	Aniba rosaeodora Ducke.
Cacao	Theobroma cacao L.

## AETHEROSTICK INFORMATION SHEET

## Aethereo®Sticks are a simple, portable, economical and effective way to enjoy the aromatherapeutic benefits of essential oils - wherever you are.

Long-lasting and safe for all ages, AethereoSticks are enjoyed by people at home, at work or school, and while traveling. AethereoSticks are widely used in hospitals for adjunctive symptom management and general well-being. Providing single-person exposure, they offer the ultimate in personal, private diffusion.

### What is in an AethereoStick?

AethereoSticks are available in a wide range of undiluted essential oils and scientifically formulated essential oil blends. These precious plant materials can help with symptom relief and help to create a healing environment, which supports our natural abilities to balance, restore, and maintain overall wellness.

### How do you use an AethereoStick?

Unscrew the outer cap. Hold the AethereoStick a few inches from your nose and take three or four slow, deep breaths. Enjoy. Repeat as desired.

### How long will an AethereoStick last?

AethereoSticks are given a nominal one year expiry date when sealed and unopened. When AethereoSticks are unsealed, opened, and in use, trials indicate that a product life of about three months can be expected, depending upon frequency of use. Due to variations in aroma intensity, some will be effective for much longer than three months, and some for less. The variables to which the product may be exposed after opening will influence the length of time the essential oil in the AethereoStick remains available.

### Built-in clip for optional hands-free use

At the request of our health care customers, we have redesigned the inner cylinder to incorporate a patent-pending built-in clip for hands-free use in hospitals. Simply remove the outer cap and slide the clip onto clothing or gown. Perfect for when the user is unable to hold the AethereoStick – including peri-op, sedation, infusion, memory care, hospice and palliative care. Or use it in hand, removing the outer cap and holding the inner cylinder a few inches from your nose.

## PRODUCT EXPIRY INFORMATION

Firefox

about:blank

### PLANT EXTRACTS INTERNATIONAL PRODUCT LIFE/EXPIRY INFORMATION

Every Plant Extracts International product carries information indicating the date of manufacture (*for example, "Made 06.16.21"*) rather than the date of expiry; and our product stock number (*for example, # 642*). In addition, bottles of undiluted essential oil are marked with the Lot (Batch) #.

While expiry dates are not always absolute or consistent because of differences in materials, use, and storage, we are often asked to provide them – thus the following:

In relation to expiry dates, the following information gives greater detail.

#### BOTTLED ESSENTIAL OILS

Unopened bottles of undiluted essential oil are given a minimum of one year expiry date. When a bottle of undiluted essential oil is opened for use, relevant hospital policy regarding expiry, safe use, and disposal of unused contents applies.

#### FORMULATED PRODUCTS

Formulated products in a carrier base, such as massage oils, bath salts, and multi-purpose sprays, are given a minimum of one year expiry date when unopened. When a formulated product is opened for use, relevant hospital policy regarding expiry, safe use, and disposal of unused contents applies.

#### AETHEROSTICKS

AethereoSticks are given a minimum of one year expiry date when sealed and unopened. When AethereoSticks are unsealed, opened, and in use, trials indicate that a product life of about three months can be expected, depending upon frequency of use. Due to variations in aroma intensity, some will be effective for much longer than three months, and some for less. The variables to which the product may be exposed after opening will influence the length of time the essential oil in the AethereoStick remains available.

*We recommend purchasing our products in quantities that give you a few weeks supply at most. Our just-in-time manufacturing practices make it unnecessary to overstock, assuring that your inventory is always as fresh as possible. This eliminates situations where newer stock may get put in front and older stock continues to age. Storage conditions can also play a role – stored in sunlight or a warm room, products will not be effective for as long. Ordering frequently will ensure that you have the freshest and most efficacious products.*

July 2021

Appendix D

Logbooks for Intervention & Control Groups

ID# \_\_\_\_\_

**AROMA INHALER STUDY**

**LOGBOOK**

**INTERVENTION GROUP**

**Directions for using your aroma inhaler and this logbook:**

**Follow these steps to use your aroma inhaler:**

1. Hold the aroma inhaler by the base
2. Twist off the cap. The inner part of the aroma inhaler with the essential oil-soaked cotton wick is part of a closed system and is not intended to be opened. All you need to do is twist off the cap
3. Hold the aroma inhaler within 3 inches of your nose
4. Breath in gently through your nose for 3 seconds
5. Hold your breath for about three seconds and then exhale gently through your mouth
6. Repeat this 3 times\* and then replace the cap and store your aroma inhaler in a cool, dry place away from children or pets. (You may repeat this breathing cycle more than 3 times each day, please remember to make a note of this in the comments section about when and why you did)
7. Use at least 3 times a day, and if you want to, use it more, but this should be recorded on the daily logbook page

**Follow these steps to use your Logbook:**

**Use your logbook to track how you are using your aroma inhaler and how you are feeling**

1. Use a new page of the logbook for each of the seven days of the study
2. If you forget or purposely do not do the aroma inhaler, please make a note with a brief reason why
3. Do not stop the study because you miss a step of using the inhaler or recording in the logbook
4. Keep your logbook in a secure place as we will collect it at the end of the study
5. Do not write important or private information that does not have to do with using your aroma inhaler in this logbook
6. Do not write your name on the logbook
7. All information provided in the logbook will be kept confidential
8. **Return within 3 days of completion**

**\*NOTE:** If you develop any uncomfortable symptoms such as a headache, stop using the aroma inhaler, recap, and retry a little later. If unpleasant symptoms continue the next time, discontinue use and contact [name], the Principal Investigator (PI), at [[contact]](mailto:[contact]).

Day 1

Please indicate each time you use your inhaler today (approximate time of day)

- I used my aroma inhaler as directed for the first time today
- I used my aroma inhaler as directed for the second time today
- I used my aroma inhaler as directed for the third time today

Any additional comments:

If you used your aroma inhaler any extra times, please indicate when and brief reason why  
(example: 2:30p, feeling stressed, and it seemed to help)

One time at the end of each day, after using the inhaler throughout your day, place an X on the line under "I feel as comfortable as possible today"

I feel as comfortable as possible today

Strongly disagree	Strongly agree
<hr/>	

Comments:

If you have any questions or comments, contact [name] at [[contact]](mailto:[contact]).  
Thank you

Day 2

Please place a check mark or X on the line each time you use your inhaler today

- I used my aroma inhaler as directed for the first time today
- I used my aroma inhaler as directed for the second time today
- I used my aroma inhaler as directed for the third time today

Comments: (example: I used my aroma inhaler an extra time today because...)

One time each day place an X on the line under "I feel as comfortable as possible today"

I feel as comfortable as possible today

Strongly disagree	Strongly agree
<hr/>	

Comments:

If you have any questions or comments, contact [name] at [[contact]](mailto:[contact]).

Thank you

Day 3

Please place a check mark or X on the line each time you use your inhaler today

- I used my aroma inhaler as directed for the first time today
- I used my aroma inhaler as directed for the second time today
- I used my aroma inhaler as directed for the third time today

Comments: (example: I used my aroma inhaler an extra time today because...)

One time each day place an X on the line under "I feel as comfortable as possible today"

I feel as comfortable as possible today

Strongly disagree	Strongly agree
<hr/>	

Comments:

If you have any questions or comments, contact [name] at [[contact]](mailto:[contact]).

Thank you

Day 4

Please place a check mark or X on the line each time you use your inhaler today

- I used my aroma inhaler as directed for the first time today
- I used my aroma inhaler as directed for the second time today
- I used my aroma inhaler as directed for the third time today

Comments: (example: I used my aroma inhaler an extra time today because...)

One time each day place an X on the line under "I feel as comfortable as possible today"

I feel as comfortable as possible today

Strongly disagree	Strongly agree
<hr/>	

Comments:

If you have any questions or comments, contact [name] at [[contact]](mailto:[contact]).

Thank you

Day 5

Please place a check mark or X on the line each time you use your inhaler today

- I used my aroma inhaler as directed for the first time today
- I used my aroma inhaler as directed for the second time today
- I used my aroma inhaler as directed for the third time today

Comments: (example: I used my aroma inhaler an extra time today because...)

One time each day place an X on the line under "I feel as comfortable as possible today"

I feel as comfortable as possible today

Strongly disagree	Strongly agree
<hr/>	

Comments:

If you have any questions or comments, contact [name] at [[contact]](mailto:[contact]).

Thank you

Day 6

Please place a check mark or X on the line each time you use your inhaler today

- I used my aroma inhaler as directed for the first time today
- I used my aroma inhaler as directed for the second time today
- I used my aroma inhaler as directed for the third time today

Comments: (example: I used my aroma inhaler an extra time today because...)

One time each day place an X on the line under "I feel as comfortable as possible today"

I feel as comfortable as possible today

Strongly disagree	Strongly agree
<hr/>	

Comments:

If you have any questions or comments, contact [name] at [[contact]](mailto:[contact]).

Thank you

Day 7

Please place a check mark or X on the line each time you use your inhaler today

- I used my aroma inhaler as directed for the first time today
- I used my aroma inhaler as directed for the second time today
- I used my aroma inhaler as directed for the third time today

Comments: (example: I used my aroma inhaler an extra time today because...)

One time each day place an X on the line under "I feel as comfortable as possible today"

I feel as comfortable as possible today

Strongly disagree	Strongly agree
<hr/>	

Comments:

If you have any questions or comments, contact [name] at [[contact]](mailto:[contact]).

Thank you

- Thank you for completing your seven-day aroma inhaler study!
- Please place your survey and logbook in the envelope provided and seal it
- Return this envelope to the Chestnut Ridge Center within 3 days of completion
- Receive a \$20 gift card
- Keep the aroma inhaler and all other study materials as our way of saying thank you!

ID# \_\_\_\_\_

**AROMA INHALER STUDY**

**LOGBOOK**

**CONTROL GROUP**

**Follow these steps to use your Logbook:**

**Use your logbook to track your comfort on each of the seven days of the study**

Day 1

One time each day place an X on the line under "I feel as comfortable as possible today"

I feel as comfortable as possible today

Strongly disagree	Strongly agree
<hr/>	

Comments:

If you have any questions or comments, contact [name] at [[contact]](mailto:[contact]).

Thank you

Day 2

One time each day place an X on the line under "I feel as comfortable as possible today"

I feel as comfortable as possible today

Strongly disagree	Strongly agree
<hr/>	

Comments:

If you have any questions or comments, contact [name] at [[contact]](mailto:[contact]).

Thank you

Day 3

One time each day place an X on the line under "I feel as comfortable as possible today"

I feel as comfortable as possible today

Strongly disagree	Strongly agree
<hr/>	

Comments:

If you have any questions or comments, contact [name] at [[contact]](mailto:[contact]).

Thank you

Day 4

One time each day place an X on the line under "I feel as comfortable as possible today"

I feel as comfortable as possible today

Strongly disagree	Strongly agree
<hr/>	

Comments:

If you have any questions or comments, contact [name] at [[contact]](mailto:[contact]).

Thank you

Day 5

One time each day place an X on the line under "I feel as comfortable as possible today"

I feel as comfortable as possible today

Strongly disagree	Strongly agree
<hr/>	

Comments:

If you have any questions or comments, contact [name] at [[contact]](mailto:[contact]).

Thank you

Day 6

One time each day place an X on the line under "I feel as comfortable as possible today"

I feel as comfortable as possible today

Strongly disagree	Strongly agree
<hr/>	

Comments:

If you have any questions or comments, contact [name] at [[contact]](mailto:[contact]).

Thank you

Day 7

One time each day place an X on the line under "I feel as comfortable as possible today"

I feel as comfortable as possible today

Strongly disagree	Strongly agree
<hr/>	

Comments:

If you have any questions or comments, contact [name] at [[contact]](mailto:[contact]).

Thank you

- Thank you for completing your logbook for the seven-day aroma inhaler study!
- Please place your survey and logbook in the envelope provided and seal it
- **Return this envelope to the Chestnut Ridge Center within 3 days of completion**
- Receive a \$20 gift card
- You will receive the aroma inhaler and all other study materials as our way of saying thank you!

## Appendix E

### Reminder Paper

#### SEVEN DAY AROMA INHALER STUDY

(Please post this in a place where you will see it each day as a reminder to use your aroma inhaler and logbook) **Thank you for your participation ☺**

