## Contents of Study Packets

1. Aroma inhaler
2. Aethereo®Stick Information Sheet
3. Cover letter (Appendix C)
4. Consent forms (2 copies)
5. Pre surveys (Comfort, Ease, and Stress)
6. Logbooks for Intervention or Control Groups (Appendix D)
7. Reminder paper (Appendix E)
8. 6 x 9 Postage paid return envelope
  - a. Post surveys (Comfort, Ease, Stress, Post Aroma)

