### CONTROL:

- v. Those randomized to the Control group (The AROMA INHALER from Control group packets is labeled with participants ID# and kept in a secure location until they complete the study. It will have been opened and demonstrated with the participant during study introduction)
  1. Left pocket (in this order)
    - a. Welcome letter
    - b. Copy of consent
  2. Right pocket (in this order)
    - a. Logbook (with dates written in)
    - b. Reminder paper
  3. Postage paid envelope (with date and instructions for return on note attached to front of the envelope)

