#### **How to use & store your aroma inhaler\***

##### **DIRECTIONS: To use 3 times daily and as desired:**

###### 1. Uncap Inhaler

Hold within 3 inches of the nose

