###### 3. Recap Inhaler & Record all uses & reactions to the inhaler in the Logbook\*\*

###### 4. Keep your aroma inhaler and logbook in a safe place. The aroma inhaler is yours to keep.

\*\*The logbook is returned at the end of this study

\*(When not in use, recap to close & store in a cool, dry place away from children and pets) It is OKAY to keep your closed inhaler in your pocket or purse and at room temperature ☺

Do not tamper with the packaging. Keep out of reach of children and animals. If you develop any adverse reactions such as a headache, stop, recap inhaler, and retry a little later. If

OFFICE OF HUMAN RESEARCH PROTECTION

unpleasant effects, such as headache continue, discontinue use and contact [name],

Investigator at [[contact]](mailto:[contact])

Thank you!

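### The only Reminder Paper shown (Appendix E) goes to controls but tells them to use the inhaler three times daily and keep it, against the plan to hold the control inhaler until the end

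*Combined protocol and SAP*

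**What the plan says.** *What the sheet says.* Appendix E asks the reader: "Please post this in a place where you will see it each day as a reminder to use your aroma inhaler and logbook". Its directions are "To use 3 times daily and as desired". It goes on with "Record all uses & reactions to the inhaler in the Logbook" and "The aroma inhaler is yours to keep". Nothing on it names an arm, and it runs to its closing line with no second version after it.

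*Who gets it.* Contents of Study Packets names separate logbooks for the two arms (Appendix D) but a single reminder paper (Appendix E). Under Documents to Leave in Participant Packet, the control list puts "Reminder paper" in the right pocket.

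*What is planned for controls.* The same control list says the "AROMA INHALER from Control group packets is labeled with participants ID# and kept in a secure location until they complete the study". Timing Of Gift Card releases the inhaler to controls after their final survey comes in. The control logbook in Appendix D asks only for a daily comfort rating and closes by promising the inhaler in the future tense.

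*How enrolment changed.* The amendment approval in Appendix G (September 2022) replaces in-person enrolment with mailed materials, moves the first sniff of the inhaler to the participant's home, and adds a meeting or call after the mailing. An October 2023 entry in Updates to Study Protocol also refers to mailed packets.

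**The concern.** A control participant is given a sheet to post at home that prescribes the active regimen. That contradicts the design, in which controls go without bergamot for the seven days. Hypotheses 1a and 1b rest on that contrast.

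What is at stake depends on whether the control has an inhaler to hand. Without one, the sheet cannot be followed. With one, a control who obeys the sheet receives the intervention while being analysed as untreated. If bergamot has an effect, the group difference shrinks. Such use would also be hard to count: the intervention logbook has tick lines for each use, while the control logbook has only a free comments space.

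**Working it through.** **Step 1: the texts side by side**

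| Topic | Appendix E, as left with controls | Rest of the plan, for controls |
|---|---|---|
| Use in the 7 days | Three times daily and as wanted | None; the logbook covers comfort only |
| Possession | The reader's own | Held by staff, given after the final survey |
| Recording | All uses and reactions | No use item in the control logbook |

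The instruction on use is a direct conflict. The statement on ownership conflicts in timing only, because controls do get the inhaler in the end.

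**Step 2: can a control act on the sheet?**

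- *In person:* the control packet starts with an inhaler, it is demonstrated, and staff then keep it. The control goes home with the sheet and no inhaler, so there is no dilution.
- *Mailed:* the packet list includes an inhaler and the sniff happens at home. The safeguard in the control list depends on staff taking the inhaler back at a visit. No visible text replaces that step for a mailed control.

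**Step 3: reproduce the planned sample size**

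Inputs from Sample Size: f = 0.25, alpha = 0.05, power 80%, 2 groups, m = 2 measurements, correlation rho = 0.50, 49 per arm.

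The plan does not name the ANOVA term, so both were tried, using the noncentral F with 1 and N − 2 degrees of freedom:

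- Between-factors: lambda = f² × N × m / (1 + (m − 1) × rho). At N = 98, lambda = 0.0625 × 98 × 2 / 1.5 = 8.17 and power is 0.808. At N = 96 power is 0.799. The smallest even N reaching 80% is therefore 98, which matches the plan.
- Group-by-time interaction: lambda = f² × N × m / (1 − rho). At N = 98, lambda = 0.0625 × 98 × 2 / 0.5 = 24.5 and power is 0.998. This term would need only 34 participants, so it is not the source of 98.

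**Step 4: illustrate dilution**

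The documents give no exposure rate. Suppose a share c of controls uses an inhaler and gets the full effect. The mean difference shrinks by (1 − c), so f becomes 0.25 × (1 − c), ignoring any change in variance. At N = 98:

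| c (assumed) | Controls of 49 | f | Power, between-factors | Power, interaction |
|---|---|---|---|---|
| 0% | 0 | 0.2500 | 0.808 | 0.998 |
| 5% | 2.45 | 0.2375 | 0.767 | 0.996 |
| 10% | 4.9 | 0.2250 | 0.721 | 0.993 |
| 20% | 9.8 | 0.2000 | 0.619 | 0.975 |

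If exposed controls got half the effect, 20% exposure would equal the 10% row (f = 0.25 × (1 − 0.20 × 0.5) = 0.225).

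**The case against.** The strongest reply is that the written procedure already prevents harm. The control list, the gift-card section and the control logbook agree that controls have no inhaler during the week, and a person without an inhaler cannot follow the sheet. For in-person enrolment this stands in full.

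For mailed enrolment, the reply is that the gap is inferred. Pages were removed from the public file, and the documents approved with the amendment are not shown. Packet contents were later changed for mailing (the consent copy was dropped), so the in-person list may not be the mailed one. The call after the mailing could also give arm-specific instructions. This stands too: withholding may be covered somewhere out of view. None of it makes the sheet right for controls.

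A reader might infer that controls were in fact contaminated, or that the trial's power falls to 62%. The documents support neither. They give no exposure rate, and the power loss appears only under an assumed rate, an assumed effect in those exposed, and one of two possible ANOVA terms. Reproducing 98 shows which option was used for sample size, not which term will be analysed.

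A reader might also take the reminders on days 1 to 3 as a second instruction to use the inhaler. The protocol gives only a summary of them, and it describes asking whether the inhaler was used, not telling anyone to use it. No template is shown, so that point carries no weight in the finding.

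**Conclusion.** The contradiction is certain on the text shown: controls are left a sheet written for inhaler users. Its consequence is conditional.

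- In-person enrolment: a wrong and confusing instruction, with no dilution.
- Mailed enrolment: a possible route to control exposure, because no visible text says how the inhaler is withheld. It is not shown to occur, and its rate is unknown. If bergamot works, any such exposure biases the comparison towards zero.

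The power figures only indicate scale. Full exposure of 5% to 20% of controls would give 77% to 62% on the between-factors test, and 97% or more on the interaction. With no exposure nothing is lost. The planned margin over 80% on the between-factors test is under one percentage point (0.808), so on that test even the 5% case falls below target.

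This should be corrected because the instruction is wrong and cheap to fix, not because damage has been demonstrated.

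**What to change.** 1. Issue a control version of Appendix E that mentions only the logbook and the daily comfort rating, or take the sheet off the control list.
2. State that, under mailed enrolment, controls hold no inhaler during the seven days and receive it after the final survey, and say how the home sniff is handled so that this holds. If pages not shown already cover this, a cross-reference is enough.
3. Make sure any message sent to controls on days 1 to 3 does not refer to inhaler use.
4. Optional: one control logbook item asking whether the study inhaler was used. The daily comments space can catch some of this, but not uniformly.

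The cost is one reprinted sheet, a check of the message text and a minor IRB amendment. Sample size and analysis do not change.
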